#### 1.2.5 Translational Studies

Every attempt will be made to recruit patients with disease that can be sampled by biopsy. In these patients, every attempt will be made to obtain tissue before the start of treatment and after the completion of the fourth or fifth dose of ixabepilone. Both

biopsies will be processed in one of three ways: (1) for immunohistochemical staining; (2) for RNA; and (3) for protein isolation, if a sufficient quantity is available. We would note here that we have extensive experience examining the effect of microtubule targeting agents on tumors both in renal cell carcinoma and in breast cancer using both immunoblot analysis and immunohistochemistry [59]. In renal cell carcinomas, we pursued a strategy validated in our laboratories that exploited the fact that alpha-tubulin can undergo several posttranslational modifications after assembly into stabilized microtubules, including acetylation and detyrosination. We had previously observed these modifications in cell culture after exposure to agents that stabilize microtubules. Our objective was to develop a straightforward and dependable assay to show tubulin target engagement in tumor tissue after treatment of patients with ixabepilone. To that end we assessed the levels of post-translationally modified alpha-tubulin in lysates of cultured malignant cell lines, as well as in both tumor tissue and peripheral blood mononuclear cells derived from patients before and after treatment with ixabepilone. Modification-specific antibodies permitted quantitative Western blot analysis. In cultured cell lines, the levels of detyrosinated (glu-terminated) and acetylated alpha-tubulin increased after microtubule stabilization induced by ixabepilone. ixabepilone treatment also induced a 2-fold to 25-fold increase in detyrosinated alpha-tubulin levels in 11 of 13 serial biopsies and a 2-fold to 100-fold increase in acetylated alpha-tubulin in 11 of 12 serial biopsies obtained from patients receiving ixabepilone. Overall, little or no difference in tubulin modifications were observed between the before and after ixabepilone treatment in lysates from their peripheral blood mononuclear cells at the time point examined. We concluded based on this experience that assessing the levels of detyrosinated and/or acetylated alpha-tubulin provides a simple and reliable assay to show target engagement by the microtubule-stabilizing agent, ixabepilone. Furthermore, this type of analyses can provide further understanding of therapeutic success or failure of microtubule-stabilizing agents in cancer therapy, since one can discern whether failure to benefit a patient by shrinking their tumor is a consequence of failure of the drug to engage its target or a consequence of a distal block to cell death – the possibility we wish to further elucidate in the current study. In breast cancer biopsies were collected at baseline and during cycle 2 from five patients (one patient had a partial response, two patients had stable disease, and two patients had progressive disease) and were confirmed by pathology to contain tumor. Four of these paired patient biopsies were analyzed by Western blot. For one patient, the baseline sample was not adequate. Increased acetylation of alpha-tubulin was seen by Western blot for all four patients, as was increased detyrosination (glu terminated alpha-tubulin). Because the protein lysates run on Western blot contain both tumor and stromal components of the biopsy, we next chose to quantify tumor changes alone by immunohistochemistry. Four of the five paired patient biopsies had tissue available for sectioning for immunohistochemistry. For one patient who had a partial response to ixabepilone, levels of acetylated alpha-tubulin were detected in both tumor and stromal cells in the baseline sample and increased in both cellular compartments with treatment. In contrast, in a patient who had progressive disease, levels of acetylated alpha-tubulin were detected only in stromal cells at baseline and increased in the stroma but were still absent in the tumor cells with treatment. Baseline levels of acetylated alpha-tubulin were present before treatment and increased after treatment in the patients with response and stable

disease, and levels of glu-terminated alpha-tubulin increased in all patients with treatment. Thus from the available paired tumor biopsies, we observed increased levels of both glu-terminated and acetylated alpha-tubulin after treatment, indicating that ixabepilone stabilized microtubules in the target tissue. Measures of stabilized microtubules may not only demonstrate a drug effect, but may also help to predict response when examined in a pretreatment specimen. Interestingly, we found that acetylated alpha-tubulin levels were higher at baseline in the tumor cells of patients whose tumors responded or in patients with stable disease than in the patient whose tumor did not respond. In the patient with progressive disease, baseline levels of acetylated alpha-tubulin within the tumor were not detectable by immunohistochemistry. Thus, our results suggest that a tumor with inherent microtubule stability might be more likely to respond to a stabilizing agent with additional microtubule stabilization and decreased proliferation. Although the small numbers of patients biopsied in this group limits our ability to make more definitive statements, these interesting observations are hypothesis generating and should be considered for additional study. This again is an observation we seek to pursue in this trial.

The following translational studies will be performed:

- 1) Immunohistochemical staining will be performed using antibodies that as described above can assess the extent of tubulin stabilization (antibodies that detect acetylated alpha-tubulin and detyrosinated (glu-terminated) alpha-tubulin. Specifically we will be looking to see if in the malignant cells, tubulin polymerization occurs following treatment with ixabepilone as evidenced by enhanced staining with the acetylated alpha-tubulin and detyrosinated (glu-terminated) alpha-tubulin antibodies. If there are normal cells in the biopsy (a likely possibility) we will be able to compare the observations in malignant cells with that in normal cells. This will allow us to determine if ixabepilone has reached its target and resulted in tubulin polymerization, by comparing the results in the post-treatment sample with those in the pre-treatment sample. This information will be valuable in analyzing the reasons for treatment failure by discriminating between an absence of an effect on the target (tubulin) versus a lack of subsequent events that leads to cell death. Because both the pre-treatment and post-treatment samples will be in blocks we will be able to easily perform additional studies, including additional immunohistochemical stains. One such stain will utilize an antibody that detects the 85kDa fragment generated when PARP cleavage occurs. We are aware of the use of this antibody in other settings, and in one center, it has been used to examine some tumor samples obtained after the administration of ixabepilone. In one patient with breast adenocarcinoma metastatic to the skin, investigators were able to demonstrate immunostaining with the antibody against 85kDa fragment 24 hours after the administration of ixabepilone. Immunostaining for p53 will also be performed [42].
- 2) RNA, and will be extracted and this will be banked. Its fate will depend on the response rates observed in this trial. If ixabepilone is found to be active in over 20% of patients, then all samples obtained will be analyzed by cDNA microarray to determine if differences exist which can discriminate responding from non-responding tumors. However, if no significant activity is observed with ixabepilone in cervical cancer, it is unlikely that cDNA microarray, which entails a

substantial amount of work, will be carried out. Also, if ixabepilone is found to be active in over 20% of patients, the expression of beta-tubulin isotypes will be determined to discern in a preliminary analysis if there is any correlation between b-tubulin isotype expression pattern and response to therapy. In NSCLC a correlation between the expression of  $\beta$ -tubulin isotypes and response to therapy has been demonstrated with reduced response to therapy found in patients with higher level of class III beta-tubulin [61, 62].

- 3) If the sample is sufficiently large, we will isolate protein and determine the extent to which tubulin polymerization has occurred using the antibodies used in the immunohistochemical analyses described above. This would be performed in a manner similar to that described for the peripheral mononuclear cells.

#### 1.2.6 Rationale for current trial

The conduct of this trial is supported by the knowledge that tubulin is an excellent target for chemotherapeutic agents, combined with the clinical success of the taxanes, and the putative advantages of the epothilones. The possibility that an agent with activity as broad as that observed with the taxanes might be active in cervical carcinoma is an exciting possibility. The recent approval of ixabepilone for the treatment of breast cancer confirms the activity of this microtubule-stabilizing agent, and its superiority over the taxanes. In addition the trial seeks to use the tissue obtained from the patients enrolled on study who undergo biopsies to further our understanding of the mechanisms of drug sensitivity clinically. As detailed, assessment of microtubule stabilization and the activation of cell death pathways will be queried to assist in understanding drug sensitivity clinically.

The treatment of metastatic and recurrent cervical carcinoma and cervical adenocarcinoma remains a difficult and challenging problem. We have treated two patients with adenocarcinoma of the cervix (described below) in which an objective tumor response was observed following treatment with ixabepilone. These patients were part of our phase I study of patients with solid tumors who had progressed after standard chemotherapy. Despite the devastating clinical outcome of the first case, in both cases presented, we were impressed with the remarkable reduction in tumor volume seen after extensive prior chemotherapy. We feel that ixabepilone will replace the taxanes in the therapy of breast cancer, and if activity is demonstrated in cervical cancer, and this activity, as that observed in breast cancer is superior to that of the taxanes, then this agent could be beneficial to women suffering from this disease, that when it presents with metastases is incurable.

The infrequent occurrence of cervical adenocarcinoma has made it difficult to evaluate the efficacy of chemotherapy in a rigorous manner. Although it is difficult to draw firm conclusions, the available data suggests that combination therapy may be better, and that as a single agent, paclitaxel may be the most beneficial chemotherapeutic agent. Given existing data demonstrating paclitaxel's efficacy in adenocarcinoma of the cervix, it is not surprising that the epothilones would be shown to have activity. However, both patients whom we treated and in whom we observed a response to therapy had received prior paclitaxel, without a response, and the demonstration of a response to ixabepilone, especially after additional chemotherapy had been administered, is

encouraging, albeit preliminary. The ultimate role of ixabepilone and multiagent chemotherapy in the treatment of adenocarcinoma of the cervix remains to be determined.

While these patients had cervical adenocarcinoma, the trial will recruit all patients with a diagnosis of cervical cancer, and will stratify patients into squamous carcinoma or non-squamous carcinoma. The latter will include patients with adenocarcinoma as well as patients with adenosquamous histology.

Furthermore while we have extensive experience examining tubulin polymerization in patients with kidney cancer, we will seek to extend those observations in these patients, while also trying to probe further the effect of ixabepilone. To that end we will also examine whether there is evidence of activation of pathways of cell death, initially by examining the activation of PARP.

## 2 ELIGIBILITY ASSESSMENT AND ENROLLMENT

### 2.1 ELIGIBILITY CRITERIA

#### 2.1.1 Inclusion criteria:

Patients must fulfill all of the following criteria to be eligible for study admission:

1. Age  $\geq$  18 years.
2. Histologic or cytologic confirmation of cervical carcinoma, squamous or non-squamous. Within the non-squamous cohort is adenocarcinoma and adenosquamous as well as non-squamous (not otherwise specified).
3. Subjects with unresectable recurrent cervical cancer are eligible.
4. Measurable disease that can be assessed using RECIST criteria.
5. Performance Status ECOG 0-2.
6. Life expectancy of 3 months or greater.
7. Suitable candidate for receiving planned therapy as evidenced by screening laboratory assessments of hematologic, renal, hepatic, and metabolic functions: platelet count  $\geq$  75,000/mm^3, absolute granulocyte count (AGC)  $\geq$  1,000/mm^3, serum creatinine  $\leq$  1.6 or a measured creatinine clearance  $\geq$  40 ml/min, SGPT and SGOT  $\leq$  2.5 x NL, and total bilirubin  $\leq$  1.5 x NL (in patients with clinical evidence of Gilbert's disease,  $\leq$  3 x NL).
8. Note: A diagnosis of Gilbert's disease will be made in the presence of (1) unconjugated hyperbilirubinemia noted on several occasions; (2) normal results from CBC count, reticulocyte count, and blood smear; (3) normal liver function test results; and (4) an absence of other disease processes that can explain the unconjugated hyperbilirubinemia.
9.  $\geq$  4 weeks from prior radiation, intravenous chemotherapy or immunotherapy;  $\geq$  6 weeks from prior nitrosourea;  $\geq$  2 weeks from a prior "phase 0 study".
10. No serious intercurrent medical illness.
11. The ability to understand and willingness to sign a written informed consent form, and to comply with the protocol.
12. Prior therapy with cisplatin or carboplatin is required.

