### 3.8 RADIATION GUIDELINES

No concurrent radiation therapy will be allowed on study.

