### 5.2 RESPONSE CRITERIA (RECIST)

#### Eligibility:

Only patients with measurable disease at baseline can have objective tumor response evaluated as an endpoint.

Measurable disease: The presence of at least one measurable lesion. If the measurable disease is restricted to a solitary lesion, its neoplastic nature should be confirmed by cytology/histology, if possible.

Measurable lesions: Lesions that can be accurately measured in at least one dimension with longest diameter  $\geq 20$  mm using conventional techniques or  $\geq 10$  mm with spiral CT scan.

Non-measurable lesions: All other lesions, including small lesions (longest diameter  $< 20$  mm with conventional techniques or  $< 10$  mm with spiral CT scan), bone lesions, leptomeningeal disease, ascites, pleural/pericardial effusion, inflammatory breast disease, lymphangitis cutis/pulmonis, cystic lesions, and also abdominal masses that are not confirmed and followed by imaging techniques.

- All measurements should be taken and recorded in metric notation, using a ruler or calipers. All baseline evaluations should be performed as closely as possible to the beginning of treatment and never more than 4 weeks before the beginning of the treatment.
- The same method of assessment and the same technique should be used to characterize each identified and reported lesion at baseline and during follow-up.

- Clinical lesions will only be considered measurable when they are superficial (e.g., skin nodules and palpable lymph nodes). For the case of skin lesions, documentation by color photography, including a ruler to estimate the size of the lesion, is recommended.

Methods of Measurement:

- CT and MRI are the best currently available and reproducible methods to measure target lesions selected for response assessment. Conventional CT and MRI should be performed with cuts of 10 mm or less in slice thickness contiguously. Spiral CT should be performed using a 5 mm contiguous reconstruction algorithm. This applies to tumors of the chest, abdomen and pelvis. Head and neck tumors and those of extremities usually require specific protocols.
- Lesions on chest X-ray are acceptable as measurable lesions when they are clearly defined and surrounded by aerated lung. However, CT is preferable.

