- For accurate objective response evaluation, ultrasound (US) should not be used to measure tumor lesions. However, US is a possible alternative to clinical measurements of superficial palpable lymph nodes, subcutaneous lesions and thyroid nodules. US might also be useful to confirm the complete disappearance of superficial lesions usually assessed by clinical examination.
- The utilization of endoscopy and laparoscopy for objective tumor evaluation has not yet been fully and widely validated. Their uses in this specific context require sophisticated equipment and a high level of expertise. Therefore, the utilization of such techniques for objective tumor response should be restricted to validation purposes. However, such techniques can be useful in confirming complete pathological response when biopsies are obtained.

Baseline documentation of "Target" and "Non-Target" lesions:

- All measurable lesions up to a maximum of five lesions per organ and 10 lesions in total, representative of all involved organs should be identified as target lesions and recorded and measured at baseline.
- Target lesions should be selected on the basis of their size (lesions with the longest diameter) and their suitability for accurate repeated measurements (either by imaging techniques or clinically).
- A sum of the longest diameter (LD) for all target lesions will be calculated and reported as the baseline sum LD. The baseline sum LD will be used as reference by which to characterize the objective tumor.
- All other lesions (or sites of disease) should be identified as non-target lesions and should also be recorded at baseline. Measurements of these lesions are not required, but the presence or absence of each should be noted throughout follow-up.

Response Criteria:

Evaluation of target lesions:

- Complete Response (CR): Disappearance of all target lesions.
- Partial Response (PR): At least a 30% decrease in the sum of the LD of target lesions, taking as reference the baseline sum LD.
- Progressive Disease (PD): At least a 20% increase in the sum of the LD of target lesions, taking as reference the smallest sum LD recorded

since the treatment started or the appearance of one or more new lesions.

Stable Disease (SD): Neither sufficient shrinkage to qualify for PR nor sufficient increase to qualify for PD, taking as reference the smallest sum LD since the treatment started.

Evaluation of non-target lesions:

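### A lesion irradiated as recently as 4 weeks before entry may be a target lesion with no evidence of growth since, so delayed radiation shrinkage can be scored as an ixabepilone response

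*Combined protocol and SAP*

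**What the plan says.** Section 2.1.1 sets three relevant entry conditions. Item 3: "Subjects with unresectable recurrent cervical cancer are eligible". Item 4: "Measurable disease that can be assessed using RECIST criteria". Item 9: at least "4 weeks from prior radiation, intravenous chemotherapy or immunotherapy".

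Section 5.2 defines measurable lesions by dimension: "Lesions that can be accurately measured in at least one dimension with longest diameter" at or above 20 mm by conventional techniques or 10 mm by spiral CT. All measurable lesions become targets, up to five per organ and ten in total. Section 5.2 then adds: "Target lesions should be selected on the basis of their size (lesions with the longest diameter) and their suitability for accurate repeated measurements". The baseline assessment must be as near to the start of treatment as can be managed and "never more than 4 weeks before the beginning of the treatment".

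A PR is a fall of at least 30% in the sum of longest diameters from baseline, confirmed at least 4 weeks later, with no new lesions and no non-target progression. Responses are reviewed independently when the study is complete.

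The only radiation rule during the study is section 3.8: "No concurrent radiation therapy will be allowed on study".

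Under section 5.4.1, each cohort stops at 0 responses in 12, otherwise continues to 37, and the drug is called active with 4 or more responses.

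**The concern.** The primary endpoint is a count of tumour shrinkage in a trial with no control arm, so nothing in the design separates shrinkage caused by ixabepilone from shrinkage already under way at entry. The protocol bars radiation during the study but leaves the after-effect of radiation given shortly before it in the endpoint.

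Section 1.2.1 shows that prior radiation is expected in this disease. It describes single-agent trials in previously irradiated patients and lower paclitaxel doses after pelvic irradiation. It gives no proportion for the population to be enrolled here.

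The decision thresholds are low. One response in 12 keeps a cohort open and four in 37 declare activity, so a few misattributed responses could change the conclusion. The opposite error is also possible: a scarred, irradiated mass in the target sum could keep a patient whose other lesions respond classified as stable.

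**Working it through.** **1. Does any rule remove the carry-over?** The provisions that come closest are:

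- *Recurrent disease (item 3) and no remaining standard options (section 6.3.5).* These describe the patient, not the lesion. A recurrence irradiated 4 weeks ago can satisfy both.
- *Pathological confirmation of a solitary lesion, if possible (section 5.2).* This shows tumour, not growth.
- *Confirmation at 4 weeks and independent review (section 5.2).* These check that shrinkage is real and lasting, not what caused it.
- *Ban on concurrent radiation (section 3.8).* This does not reach radiation that ended before entry.

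None of them closes the gap.

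**2. How much of the sum must the irradiated lesion make up?** Let w be its share of the baseline sum.

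- *False PR, other lesions unchanged:* the irradiated lesion must shrink by 0.30/w. At w = 1 that is 30%; at w = 0.5 it is 60%; below w = 0.30 it cannot happen.
- *Masked PR, irradiated lesion fixed:* the other lesions must shrink by 0.30/(1 − w). At w = 0.5 that is 60%; above w = 0.70 a PR cannot be reached.

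Both errors are possible, and both need the irradiated lesion to be a substantial part of the sum.

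**3. Reproduce the plan's design.** Inputs from section 5.4.1: n1 = 12, n = 37, stop at 0/12, active at ≥4/37, p0 = 0.05, p1 = 0.20, α = β = 0.10. With X1 ~ Bin(12, p) and X2 ~ Bin(25, p):

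- P(stop early) = (1 − p)^12
- P(active) = Σ over x = 1 to 12 of P(X1 = x) × P(X2 ≥ 4 − x)

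At p = 0.05, P(stop) = 0.95^12 = 0.540, which matches the stated 0.54.

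P(active) = 0.3413 × 0.1271 + 0.0988 × 0.3576 + 0.0173 × 0.7226 + 0.0022 = 0.0434 + 0.0353 + 0.0125 + 0.0022 = 0.093. The last term is P(X1 ≥ 4).

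At p = 0.20, P(active) = 0.902. The design is correct for its inputs.

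**4. Add an assumed carry-over to an inactive drug.** The documents give no rate; 1 to 3 percentage points is an assumption.

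| Apparent response rate | P(cohort opens stage 2) | P(called active) |
|---|---|---|
| 5% (none) | 0.460 | 0.093 |
| 6% | 0.524 | 0.151 |
| 7% | 0.581 | 0.219 |
| 8% | 0.632 | 0.294 |

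**5. The same in patients.** Suppose exactly one of 37 patients has a carry-over PR, in random order, and the other 36 respond at 5%.

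- *In the first 12 (probability 12/37):* stage 2 opens for certain, and at least 3 of the other 36 must respond. Probability 0.268.
- *In the last 25 (probability 25/37):* at least 3 of the other 36 must respond, with at least one among the first 12. Probability 0.205.

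Total: 12/37 × 0.268 + 25/37 × 0.205 = 0.087 + 0.139 = 0.226.

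**6. The opposite direction.** If masking lowered the observed rate of a truly 20% active drug to an assumed 18%, power would fall from 0.902 to 0.857.

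**The case against.** The strongest reply is that the existing text limits the problem, and in several respects it does.

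A reader might infer that the baseline scan can predate the end of prior radiation or IV chemotherapy. It cannot. Those therapies end at least 4 weeks before entry, imaging falls within 4 weeks of entry (section 2.2), and section 5.2 sets the same limit before treatment. The scan is therefore at or after the end of therapy, and section 5.2 already asks for it to be as late as practicable. No new scan-timing rule is needed. The gap remains, because shrinkage continuing after a correctly timed scan is still counted.

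A reader might also extend the point to chemotherapy with equal force. Item 12 does say "Prior therapy with cisplatin or carboplatin is required", and progression afterwards is not required. But a patient still regressing on platinum fits poorly with recurrent disease and no standard options left. A rule requiring growth since the last systemic therapy would apply to every patient, in a trial that stops if fewer than 12 enrol in 9 months (section 5.4.2).

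It is also fair to say that size ranking matters only above the caps of five and ten lesions, and that one shrinking lesion among several may not move the sum by 30%. Both points reduce how often the error occurs. Neither prevents it in a patient whose measurable disease is mainly or only an irradiated mass.

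**Conclusion.** The gap holds for radiation. Followed as written, sections 2.1.1 and 5.2 let an irradiated lesion with no evidence of regrowth enter the target sum, and a confirmed fall of 30% in that sum would be a PR whatever its cause.

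The size is not known. Under an assumed 1 to 3 points of carry-over, the per-cohort false-positive probability goes from 0.093 to 0.15–0.29 against the stated 0.10. These figures illustrate how sensitive the rule is; they do not estimate the bias. They also model inflation alone. A reader might conclude that the trial is biased towards activity, but the documents do not support that, because non-shrinking residuals push the other way and neither frequency is given.

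The sample size and stopping rule are not in question. This is an inexpensive improvement to the primary endpoint that should be made.

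**What to change.** In section 5.2, under measurable disease and target-lesion selection, state that a lesion in a previously irradiated field counts as measurable and may be a target only if it is new, or imaging shows it has grown, since that radiation ended. Otherwise record it as non-target. Refer to this rule from item 4 of section 2.1.1. Add a field for prior radiation sites to the baseline tumour form.

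This deals with both errors. A non-target lesion does not enter the sum, and under the section 5.2 response table its persistence does not prevent a PR.

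For systemic therapy, at most record whether disease progressed after the last regimen and report responses by that status, without making it an entry condition.

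The cost is a short amendment and one or two form fields. Patients whose only measurable lesion was irradiated and has not grown would wait for documented growth or not be enrolled. The documents do not say how many that would be, and the 9-month accrual rule makes it worth estimating beforehand. The 12/37 design is unchanged.
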